## **3. Research Methods and Statistical Considerations:**

### **Research Methods:**

This will be a multi- center retrospective observational comparison study.

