### **Study Population:**

All patients at risk for stroke or thromboembolism that demonstrated any degree of the significant leak on follow up TEE imaging at least 4-6 weeks following either epicardial, endocardial, or surgical LAAC were included in this study population. All patients were evaluated and followed with imaging, and per investigators' respective clinical judgement, then proceeded to have an intervention for leak closure with either detachable embolization coils, vascular plugs/CSO, or RFA.

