### Exclusion Criteria:

- Patients not undergoing leak closure after incomplete LAAC
- Patients unable to complete 45-day follow-up imaging for reevaluation of LAA leak
- Patients unable to consent

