## **Secondary Endpoints:**

1. To compare the reduction/rates of TE events and procedure-related complications (DRT, pericardial effusion/cardiac tamponade, or CVA/TIA) in patients after successful PDL closure with any of the three closure modalities
  - a. Periprocedural complications occurring from Postoperative day #0 – day 7
  - b. Delayed procedure-related complications and adverse events within 90 days of procedure

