## **Informed Consent:**

Given that this study was observational and retrospective in design, no informed consent was obtained or required. Patients who met inclusion/exclusion criteria were de-identified and added to word documents/excel spreadsheets.

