## **Data/Variable Points for Collection:**

- Age
- Sex
- Height
- Weight
- BMI
- Diabetes (y/n)
- Smoking (y/n)
- Dyslipidemia (y/n)
- Prior stroke/TIA (y/n)

- Prior deep venous thrombosis/pulmonary embolism (y/n)
- Ejection Fraction
- History of CAD (y/n)
- Congestive heart failure (y/n)
- Chronic Kidney Disease (y/n)
- Type of Atrial Fibrillation (paroxysmal, persistent, permanent)
- Baseline antithrombotic regimen (aspirin, clopidogrel/prasugrel/ticagrelor, warfarin, direct oral anticoagulant, heparin)
- TIA/stroke after Watchman
- History of major bleeding
- High Fall risk (y/n)
- Previous major bleeding (y/n)
- Previous minor bleeding (y/n)
- Thromboembolism while on oral anticoagulant
- CHA2DS2-VASc Score
- HAS-BLED Score
- Time passed since LAA closure (months)
- Type of LAA Closure (watchman/watchman FLX, amulet, lariat, surgical ligation, atriclip)
- Device Size (if applicable)
- Thrombus on device (y/n)
- Peri-device/central leak size in mm
- Acute success (end of procedure closure) (y/n)
- Procedure duration (minutes)
- Flourosopy time (minutes)
- Contrast usage (mL)
- Hospital length of stay
- Type of procedural anesthesia (general vs light sedation vs local)
- Procedural imaging (TEE, ICE, or both)
- Devices attempted
- Devices deployed
- Combination procedures (combined AF ablation, or LAA occlusion + AF ablation)
- Size/number of devices (plugs/coils)
- Major procedural complications from postoperative day 0-7: stroke, TIA, air embolism, myocardial infarction, cardiac tamponade, device embolization, ventricular tachycardia
- Minor procedural complications from postoperative day 0-7: pericardial effusion
- Complications seen within 90 days of the procedure: cardiovascular death, non-cardiovascular death, stroke/TIA, pericarditis
- Follow-up transesophageal echocardiogram time (months)
- Size of leak at follow up (in mm)
- Follow-up time
- Follow up antithrombotic regimen

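### The exclusion of patients unable to consent contradicts the statement that no consent was sought, and if applied after the procedure it could remove patients because of the outcome

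*Combined protocol and SAP*

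**What the plan says.** All references are to the combined protocol and SAP.

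- **Research Methods** describes a "multi- center retrospective observational comparison study".
- **Exclusion Criteria** lists three grounds. The last is "Patients unable to consent". No type of consent, time point or assessor is given.
- **Informed Consent** states: "Given that this study was observational and retrospective in design, no informed consent was obtained or required". It continues: "Patients who met inclusion/exclusion criteria were de-identified and added to word documents/excel spreadsheets". The exclusion list is therefore the filter through which patients reach the dataset.
- **Study Population** says that all patients with the qualifying leak "were included in this study population", and sets no condition about consent.
- **Secondary Endpoints** covers thromboembolic events and "procedure-related complications (DRT, pericardial effusion/cardiac tamponade, or CVA/TIA"), with a window to day 7 and a window to 90 days.
- **Data/Variable Points for Collection** includes "Complications seen within 90 days of the procedure: cardiovascular death, non-cardiovascular death, stroke/TIA, pericarditis".

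**The concern.** A criterion about ability to consent needs an occasion on which consent is asked for. The plan says there was none. Each centre is left to decide what the line means, and it does so from records in which the outcomes have already occurred.

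One available reading is capacity at the time of data collection. On that reading, the patients most easily classed as unable to consent are those who died or had a disabling stroke after leak closure. Stroke belongs to a secondary endpoint, and death is a collected 90-day outcome. Excluding such patients would be selection on the outcome. The planned analysis could not correct it, because these patients would never enter the dataset. The Objectives describe different centres using different modalities, so different local readings could also shift the event rates between modalities.

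**Working it through.** **1. The passages side by side.**

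| Section | What it implies about consent |
|---|---|
| Exclusion Criteria | Ability to consent is assessed, and failing it excludes the patient |
| Informed Consent | Nobody was asked, and nobody needed to be |
| Informed Consent, next sentence | Entry depends on meeting the same inclusion and exclusion criteria |
| Study Population | All patients with the leak were included, with no consent condition |

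The first two rows cannot both describe what was done. No other section resolves them.

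**2. What each reading does to the data.**

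- *Consent to the closure procedure, or capacity judged before it:* the decision comes before the outcome, so no outcome-driven removal follows.
- *Line never applied:* no removal.
- *Capacity judged from the record after the procedure:* death and disabling stroke become grounds for exclusion.

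The documents do not say which reading was used.

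**3. Which outcomes are exposed.** CVA/TIA is named under Secondary Endpoints. Death is named only in the data list, among complications within 90 days. Closure of the leak does not itself determine capacity to consent, so the primary endpoint is touched at most indirectly.

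**4. Size.** The plan states no event rate and no number excluded, so there is no figure to reproduce and none can be derived. The following only illustrates the mechanism. The planned total of 160 comes from Sample Size; p and f are assumptions.

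Let p be the true 90-day risk of stroke or death and f the share of patients with the event who are excluded as unable to consent. Assume no patient without the event is excluded. Then

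observed rate = p(1 − f) / (1 − pf)

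| Assumed p | Expected events (160 × p) | f = 0 | f = 0.25 | f = 0.50 | f = 1 |
|---|---|---|---|---|---|
| 2% | 3.2 | 2.0% | 1.5% | 1.0% | 0% |
| 5% | 8.0 | 5.0% | 3.8% | 2.6% | 0% |
| 10% | 16.0 | 10.0% | 7.7% | 5.3% | 0% |

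For example, at p = 5% and f = 0.50: 0.05 × 0.50 / (1 − 0.025) = 0.025 / 0.975 = 2.6%.

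The same formula shows the differential case. Two modalities with the same true risk of 5% would show 5.0% and 2.6% if the criterion removed no event patients in one and half of them in the other. The column f = 0 covers both harmless readings in step 2.

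The 160 is an upper bound on the denominator, because the secondary endpoint is framed for patients after successful closure.

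**The case against.** The strongest reply is that the two statements largely cancel. If no consent was sought, there was no step at which anyone could fail, and the line is probably leftover template wording with no effect. Collecting deaths and strokes to 90 days suggests that the authors expected such patients in the dataset, and Study Population mentions no consent condition. This stands as a plausible reading. The plan does not confirm it, though, and the Informed Consent section itself says that patients entered by meeting the listed criteria.

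A second reply is that the same list already excludes patients who could not complete 45-day imaging. Deaths before that imaging, and many early disabling strokes, are lost by that route whatever happens to the consent line. This stands too. The consent line can add only the remainder, mainly later events and disabled patients who were still imaged.

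Two stronger readings are tempting:

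- A reader might infer that inability to consent can only have been judged from the patient's later condition. The documents do not support this, because they fix neither the type nor the time of consent.
- A reader might infer that one excluded stroke would remove half or all of the expected events. The arithmetic would be 160 × 90 / 365.25 = 39.4 patient-years, and at an assumed 2 to 5 events per 100 patient-years, 0.8 to 2.0 expected events. The rate has no source in the plan. A constant rate also ignores the clustering that is possible in days 0 to 7. The conclusion further presupposes that a disabling stroke occurred and was excluded, so it does not measure the effect of this criterion. Several components of the endpoint, such as TIA or pericardial effusion, do not by themselves remove capacity.

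**Conclusion.** The contradiction is certain. It sits in an eligibility rule, and nothing elsewhere in the plan resolves it. Bias is possible but not shown: it requires that at least one centre applied the criterion after the procedure. If so, the secondary thromboembolic and complication rates and the collected deaths could be understated, perhaps unequally by modality. If the criterion was judged before the procedure or never used, there is no outcome-driven distortion.

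The size cannot be computed from the documents; the table above rests on assumed values of p and f. The plan should be corrected because a reader cannot tell a harmless reading from a biasing one, and removing the doubt costs very little.

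**What to change.** 1. Delete the consent bullet from the Exclusion Criteria so that it agrees with the Informed Consent section.
2. Ask each centre to check its source records for anyone excluded on this ground, and include those who are otherwise eligible. Amending the text alone is not enough, because the Informed Consent section is written in the past tense and selection may already have taken place.
3. Report the number excluded on this ground by modality, including when it is zero. A zero would settle the matter.

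The cost is a one-line amendment and a re-screening effort that should be small, although the number of records is not given. The observed event rate may rise slightly. This change does not bring back early deaths and strokes lost through the 45-day imaging exclusion, which is a separate matter.

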### **Primary Endpoints:**

1. To compare the efficacy of the three PDL closure modalities in patients with prior LAAC

## **Secondary Endpoints:**

1. To compare the reduction/rates of TE events and procedure-related complications (DRT, pericardial effusion/cardiac tamponade, or CVA/TIA) in patients after successful PDL closure with any of the three closure modalities
  - a. Periprocedural complications occurring from Postoperative day #0 – day 7
  - b. Delayed procedure-related complications and adverse events within 90 days of procedure

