## **2. Objectives:**

### Primary Objective:

Our main objective is to collect data from multiple different centers that use different modalities to currently treat either central or peri-device leaks that occur after incomplete LAA closure, and compare each modality in their efficacy and safety outcomes.

Primary Outcome: To compare the efficacy of the three current methods of PDL closure modalities in patients with prior incomplete LAAC.

Secondary Outcome: To compare the rates or reduction of rates of thromboembolic events and procedure-related complications in patients after successful PDL closure with any of the three closure modalities.

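### The complications named in the secondary endpoint do not match those collected: device embolization and other events are collected but not named, and DRT is named but has no dated outcome field

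*Combined protocol and SAP*

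**What the plan says.** The Primary Objective is to "compare each modality in their efficacy and safety outcomes". Study Population gives the modalities as an "intervention for leak closure with either detachable embolization coils, vascular plugs/CSO, or RFA".

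Secondary Endpoints names the safety outcome, beside thromboembolic events, as "procedure-related complications (DRT, pericardial effusion/cardiac tamponade, or CVA/TIA", and restricts it to patients whose leak was closed successfully. It has two sub-items: (a) "Periprocedural complications occurring from Postoperative day #0 – day 7" and (b) "Delayed procedure-related complications and adverse events within 90 days of procedure".

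Data/Variable Points for Collection lists what is abstracted:

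- Days 0-7, major: "Major procedural complications from postoperative day 0-7: stroke, TIA, air embolism, myocardial infarction, cardiac tamponade, device embolization, ventricular tachycardia".
- Days 0-7, minor: pericardial effusion only.
- Within 90 days: "Complications seen within 90 days of the procedure: cardiovascular death, non-cardiovascular death, stroke/TIA, pericarditis".
- Device thrombus: "Thrombus on device (y/n"), placed between the LAAC device size and the leak size, with no time point.

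Statistical Analysis defines no safety composite and does not say which list governs.

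**The concern.** Safety by modality is part of the main objective, yet the plan supports two different complication rates. One follows the bracket and the other follows the collection list. If the choice is left open, it can be made after the data are seen.

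Device embolization matters most among the mismatches. The plan classes it as major. Two of the three modalities place a new closure device and RFA does not, so this component bears unequally on the groups being compared. Beyond day 7 the problem is one of data as well as definition, because an embolization found at the 45-day imaging has no complication field. DRT has the reverse problem: it is named as an outcome, but no dated item separates thrombus present before leak closure from thrombus that appeared afterwards.

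**Working it through.** **1. The plan's own figure.** The only design figure is the total of 160 patients (Sample Size). It comes with no event rate, effect size, power or split by modality, so it cannot be re-derived. This point does not depend on it.

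**2. The two lists side by side.**

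| Event | Named in the endpoint bracket | Day 0-7 field | 90-day field |
|---|---|---|---|
| DRT | yes | no | no (one undated thrombus item) |
| Pericardial effusion | yes | yes, minor | no |
| Cardiac tamponade | yes | yes, major | no |
| Stroke/TIA | yes | yes, major | yes |
| Device embolization | no | yes, major | no |
| Air embolism, myocardial infarction, ventricular tachycardia | no | yes, major | no |
| Cardiovascular and non-cardiovascular death | no | no | yes |
| Pericarditis | no | no | yes |

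Only stroke/TIA is both named in the endpoint and collected in both windows.

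**3. How many embolizations could be left out.** The documents give no embolization rate. Assume equal thirds, so 160 × 2/3 ≈ 107 patients receive a coil or plug/occluder and 160/3 ≈ 53 receive RFA. Let e be the rate of embolization of the newly placed device, 0.5% to 3%, and zero with RFA. Expected events are n × e, and the chance of at least one is 1 − (1 − e)^n.

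- e = 0.5%: 107 × 0.005 = 0.54 events; 1 − 0.995^107 = 0.42.
- e = 1%: 107 × 0.01 = 1.07 events; 1 − 0.99^107 = 0.66.
- e = 3%: 107 × 0.03 = 3.21 events; 1 − 0.97^107 = 0.96.

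Other splits do not change the picture. With 80 device patients the range is 0.4 to 2.4 events, and with 130 it is 0.65 to 3.9.

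**4. Direction.** Adding embolization alone moves the device-minus-RFA risk difference by +e, that is +0.5 to +3 points. The other unlisted events (air embolism, infarction, ventricular tachycardia, death, pericarditis) could be more frequent with RFA. Let r be that excess, assumed to be 0 to 3%. Adding every unlisted event moves the difference by e − r:

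- lowest: 0.5 − 3 = −2.5 points;
- highest: 3 − 0 = +3 points;
- zero when r = e.

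The sign is not fixed by anything in the documents.

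**5. What a test could show.** With an assumed 5% base rate, 107 versus 53 patients and two-sided alpha 0.05 (normal approximation), power to detect a difference of 1, 2 or 3 points is about 4%, 6% and 9%. Whether these events are seen depends on how they are defined and tabulated, not on a p-value.

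**6. Who is counted.** The safety endpoint covers patients after successful closure. A patient whose device embolized may not count as a success, so adding the component to the list may still miss the event.

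**The case against.** The strongest reply is that embolization is already in the plan. It is collected for days 0-7, the same window as sub-item (a), so the collection list can be read as the working definition of (a). Sub-item (b) goes beyond the bracket by adding adverse events. On that reading the bracket is only illustrative. This is a possible reading, but the documents do not adopt it. The bracket is worded as a complete list, nothing says which list governs, and no reading of (b) recovers an embolization after day 7 that has no field.

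A reader might go further and infer that the safety comparison as a whole is tilted against RFA. The documents do not support that, for three reasons:

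- The bracket counts DRT, which is itself device-related, although the field for it is weak.
- It also leaves out events that are not specific to an implant, and some of these could be more frequent with RFA.
- The documents do not say that only the coil and plug/occluder groups can have device embolization. RFA patients may carry an LAAC device from the index procedure. The asymmetry holds for embolization of the newly placed closure device.

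It would also be too simple to replace the bracket with the listed major and minor complications. DRT is in neither of those lists and would drop out.

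**Conclusion.** The two safety lists disagree and must be reconciled. Taken literally, the endpoint leaves out a complication that the plan classes as major, the plan has no field for that complication after day 7, and DRT cannot be dated as an outcome. Omitting embolization of a new closure device, taken alone, favours coils and plugs/occluders over RFA. The net direction across all unlisted events is unknown, at about −2.5 to +3 points under the assumed rates.

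The size is small in counts: about 0.5 to 3.2 embolizations among 107 device patients, on an assumed equal split and assumed rates of 0.5% to 3%. In a study of 160 patients, a few major events can still change how a modality's safety reads. The mismatch itself needs no assumption, since it follows from the text. This is a definitional fault in a secondary endpoint that is worth correcting; a biased comparison has not been shown.

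**What to change.** - Define the complication endpoint as the union of the Secondary Endpoints bracket and the complications under Data/Variable Points for Collection, keeping DRT. State that this one list governs.
- Report each component by modality, for days 0-7 and within 90 days.
- Add device embolization and a dated post-procedure DRT item to the 90-day field. The other day 0-7 components, including effusion and tamponade, also have no 90-day item; add them, or state that they are reported for days 0-7 only.
- Count complications in all patients in whom leak closure was attempted, not only those with successful closure.

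The day 0-7 data are already planned, so the change amounts to a revised endpoint definition and a few added items in a retrospective chart review. The cost is slightly more abstraction and a somewhat higher stated complication rate.

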### **1. Background**

Left Atrial Appendage (LAA) Closure (LAAC) is a potent technique of LAA isolation and exclusion for stroke prevention in patients with atrial fibrillation, with evidence from the PROTECT-AF and PREVAIL-AF trials, including their 5-year follow-up assessments, solidifying LAAC as a viable option in these patients with comparable stroke reduction in comparison to oral anticoagulation (OAC) as well as a reduction in bleeding risk, hemorrhagic CVA, and mortality [1-3]. However, the surge in the multiple methods of LAA exclusion has also brought to attention postprocedural complications specific to LAAC, namely, peri-device leaks (PDL) [4]. The stroke implication and classification of PDL itself still lacks consensus, with an increased thromboembolic (TE) potential due to PDL seen in patients with LARIAT and surgical ligation procedures, yet no statistically significant relationship seen in percutaneous and endocardial LAA closure approaches [5-9]. PDL > 5mm has been widely accepted as clinically significant, although there remains limited data with no current established guidelines. [5, 6, 10]. Placement of a septal occluder device such as Amplatzer Vascular Plug, Detachable embolization coils, Gore Cardioform Septal Occluder (CSO; W.L. Gore and Associates, Newark DE), and radiofrequency ablation (RFA) have all emerged as options to resolve residual PDL and post-surgical/ligation leaks [5, 10-12]. However, there exists no head-to-head comparison between these modalities. Given their emergence, we proposed a multi-center observational study to further assess and evaluate these three treatment modalities for their efficacy for leak closure, assessment of pre-, peri- and post-procedural characteristics after leak closure, TE events, and bleeding risk, and complication rates.

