### Inclusion Criteria:

- patients at risk for stroke or thromboembolism that demonstrated any degree of the significant leak on follow up TEE imaging at least 4-6 weeks following either epicardial, endocardial, or surgical LAAC
- Patients undergoing any form of eccentric or centric/central leak closure with available modalities (detachable embolization coils, vascular plug/septal/ASD occluders, or RF Ablation). Criteria for this was made based on the judgement of the operator, with no specific cutoffs for leak size, follow-up time from LAAC to leak closure, etc)
- Age greater than 18 years

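### The TE and complication comparison is worded for successfully closed patients only; success is tied to no variable, and the plan's safety aim carries no such condition

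*Combined protocol and SAP*

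**What the plan says.** The restriction appears twice. In Section 2 (Objectives) the secondary outcome is "To compare the rates or reduction of rates of thromboembolic events and procedure-related complications in patients after successful PDL closure". In Section 3 (Secondary Endpoints) the comparison is again made "in patients after successful PDL closure with any of the three closure modalities", with an early window ("Periprocedural complications occurring from Postoperative day #0" to day 7) and a later one reaching 90 days.

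Elsewhere the aim carries no such condition. The Background lists "TE events, and bleeding risk, and complication rates" among the things to be assessed, and the main objective is to "compare each modality in their efficacy and safety outcomes". The inclusion criteria admit "Patients undergoing any form of eccentric or centric/central leak closure with available modalities", whatever the result.

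No section defines successful closure. Two candidates exist. The data list has a yes/no item for acute success, judged at the end of the procedure. Statistical Analysis names three leak categories at follow-up, without cut-offs. Neither is linked to the endpoint. The data list collects day 0-7 and 90-day complications with no restriction to successful cases, and Statistical Analysis names no safety population.

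**The concern.** Success is a result of the procedure and lies close to the primary outcome, which is efficacy of leak closure. Restricting the safety comparison to successes selects patients on something that happens after treatment and may differ by modality.

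Failure and complication can also be one event. A tamponade that ends the procedure before the leak is closed would be an example from the endpoint's own list. A device that embolizes and is not replaced would be another; the data list counts embolization as a major day 0-7 complication, although the endpoint's bracketed list does not name it. Under the literal wording such events could go uncounted in the comparison meant to capture them.

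The undefined term is a second problem. End-of-procedure success and closure at follow-up imaging can select different patients, so two analysts could report different safety denominators from the same data.

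The groups are already open to confounding, since patients, per the investigators' "respective clinical judgement, then proceeded to have an intervention for leak closure", and no adjustment is planned. The success condition does not cause that. It adds a further selection, one that wording alone can remove.

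**Working it through.** **Text check**

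1. Both statements of the secondary comparison carry the success condition. No other section overrides it.
2. The Background and the main objective state the safety aim without it. This is the substantive mismatch.
3. If success means the acute item, it is fixed at the end of the procedure. If it means closure on the 45-day imaging, it is fixed after the whole day 0-7 window and about halfway through the 90-day window (45/90). The plan does not say which.

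**Illustration**

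The plan has no figure to reproduce here. Its only relevant number is the total of 160 (Sample Size), given without a split, success rate or complication rate. Everything else below is assumed: equal groups (160/3 = 53.3), success *s* of 95%, 85% or 75%, a risk after success *c1* of 3%, and a risk after failure *c0* of 0% to 20%.

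- Patients outside the comparison if *s* applied to all: 160 × (1 − *s*) = 8, 24 or 40.
- Rate in all treated patients: *R* = *s·c1* + (1 − *s*)·*c0*. The success-only rate is *c1*, so the gap is *R* − *c1* = (1 − *s*)(*c0* − *c1*).
- Share of events left out: (1 − *s*)·*c0* / *R*.

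Each cell gives *R*, with the share of events left out in brackets. The success-only rate is 3% in every cell.

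| Risk after failure | *s* = 95% | *s* = 85% | *s* = 75% |
|---|---|---|---|
| 0% | 2.85% (0%) | 2.55% (0%) | 2.25% (0%) |
| 3% | 3.00% (5%) | 3.00% (15%) | 3.00% (25%) |
| 10% | 3.35% (15%) | 4.05% (37%) | 4.75% (53%) |
| 20% | 3.85% (26%) | 5.55% (54%) | 7.25% (69%) |

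Middle case: 0.15 × (10 − 3) = 1.05 points, or 0.0105 × 53.3 = 0.56 patient per modality.

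Contrast between modalities: with 95% against 75% success and a 10% risk after failure in both, the rates in all treated patients differ by 4.75 − 3.35 = 1.40 points, while the success-only rates do not differ. If success is 90% in every modality and the risk after failure is 10%, all three rates are 0.90 × 3 + 0.10 × 10 = 3.7%. The contrast is then undistorted, but 0.10 × 10 / 3.7 = 27% of events are left out.

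Precision: the standard error of a 3% rate in 53 patients is √(0.03 × 0.97 / 53) = 2.3 points. For the 1.40-point contrast it is √[(0.0335 × 0.9665 + 0.0475 × 0.9525) / 53] = 3.8 points.

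**The case against.** The strongest reply is that the phrase is loose wording for after the procedure. The unrestricted complication items, the absence of a success-only analysis set and the unconditional objective all point that way. This stands as a plausible reading, so a reader should not infer that the sponsor plans to exclude complications of failed closures. But the endpoint says otherwise in two places, and an analyst following it would apply the restriction.

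It can also be said that an endpoint population narrower than the enrolled one is not in itself a contradiction. That is right: the inclusion criteria alone prove nothing. Nor does the day 0 start of the early window. On the acute reading, success may already be known when that window opens, unless events during the procedure count as day 0.

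The acute-success item is the only data item that uses the word, so one cross-reference would supply the definition. This is fair, but the cross-reference is missing, and it would not remove the selection.

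Finally, every rate in the illustration is assumed, and the effects shown are small beside the sampling error. This is conceded. The point rests on the mismatch and the undefined population, not on a predicted effect. For TE events, what happens once a leak is sealed is also a legitimate question, which is why that analysis should be kept as an addition.

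**Conclusion.** The point holds as a defect of wording with a real consequence if followed: the stated safety comparison is conditioned on an undefined post-procedure result, against the plan's own unconditional aim. It should be corrected before analysis.

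Its size is unknown. Over the assumed range in the table, the success-only rate runs from 0.75 points too high (3.00 − 2.25) to 4.25 points too low (7.25 − 3.00). It is unbiased when risk is the same after success and failure. The contrast between modalities is undistorted when success rates and both risks are equal across them.

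Three stronger readings are tempting and unsupported:

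- That the comparison will be biased in a particular direction. The documents give no rates from which to say so.
- That patients must be analysed by the first modality tried, with device order recorded. No section describes crossover between modalities, and the devices-attempted item could mean sizes or models within one modality.
- That correcting the wording yields the rate in all attempted closures. Patients are excluded under "Patients unable to complete 45-day follow-up imaging for reevaluation of LAA leak", so everyone enrolled has already passed an imaging condition. That is a separate matter.

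**What to change.** - In Section 2 (secondary outcome) and Section 3 (Secondary Endpoints), replace *successful* with *attempted* before PDL closure.
- State in Statistical Analysis that day 0-7 and 90-day complications and TE events are compared in all enrolled treated patients, by modality.
- Keep any TE analysis after successful closure as a labelled additional analysis, and name the variable that defines success, for example the acute-success item if that is what is meant.
- State as a limitation that enrolled patients have already met the 45-day imaging condition, so the change does not recover events in patients excluded for missing imaging.

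Cost: the complication items and acute success are already on the collection list, so no new data item is needed. If all treated patients were meant from the start, only the wording changes. The downside for the sponsor is that reported complication rates may be less favourable.
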